**Specified Safety Measures:** Post-operative bleeding and infection occurred at low frequencies and below the literature-defined thresholds. Two brain infections were observed: culture-negative ventriculitis, surgical subject and culture-negative meningitis, medical subject. Both resolved without consequence. Recurrent bleeding rate was 5% overall: surgical, 2.65% (CI 0.07, 13.5), medical, 6.2% (CI 2.0, 13.8); pilot, 11%; randomized surgical, 3.7%; and randomized medical, 2.6%. It is difficult to attribute bleeding to the procedure or the drug; however, bleeding sites were frequently associated with the hematoma or catheter, preserving the need for caution of MIS+rt-PA as a trigger for increased likelihood of bleeding. MISTIE III will provide a better estimate of these rates. The overall rate of rebleeding (3.7%) compares well to the 10%-17% rate in other surgical and MIS trials.

[figure not shown]
**Edema:** Edema is an early indicator of tissue injury and is measured more easily in humans than cell death and ischemia. In MISTIE II, the protocol prospectively tested

[figure not shown]
the idea that clot reduction would lead to edema reduction as is observed in animals and preliminary data. Analysis of perihematomal regions of MISTIE II surgical subjects, utilizing a validated method, shows a reduction of 22 ml of edema when compared to medical subjects in the same time frame ( % reduction of 22±35 % surgical vs. increase of 47±46% medical). This finding is consistent with the reduction of toxic metabolic injury seen in animal models and inconsistent with a small number of prior “convenience samples” and clinical reports demonstrating an increase in edema after exposure to rt-PA. The Phase III will confirm the consistency of benefit across a broad population, the degree to which hematoma and edema reduction relates to improved functional performance, and the possible cellular basis of a beneficial effect.

**Functional Outcome Benefit:** ICH recovery requires more time than recovery from

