#### 4. Study Procedures

[figure not shown]
MTI:M3 is a prospective and observational, nested study within the MISTIE III randomized controlled clinical trial. This design provides tremendous leverage of the existing workload for MISTIE III, promising major insight into neuroimaging and genetic and inflammatory biomarkers of ICH pathophysiology and response to surgical intervention without affecting the execution of the parent study.

The primary goal of MTI:M3 is to determine whether radiologic and genetic and inflammatory marker data can help identify those ICH patients most likely to undergo successful clot reduction after the MIS intervention and most likely to derive clinical benefit from the procedure. Details of MISTIE III are not reprinted here. Incorporation of MTI:M3 will require an additional informed consent section in the MISTIE III consent for lab draw and collection of hematoma fluid from the collection bag/chamber. All patients enrolled in MISTIE will be eligible for MTI:M3.

- a. The study will be completed as part of the participants' hospitalization and follow-up.
- b. Imaging required for the MTI:M3 study will be done as part of the MISTIE III protocol. Image files will be uploaded to the MISTIE III coordinating center via the electronic data capture system. Image files collected from subjects who also consent to MTI:M3 will then be de-identified and electronically transferred to MTI:M3 investigators for analysis as described below in section 6.
- c. There are 2 types of blood draws:
  - (i) A daily blood draw (two teaspoons, 12 mL) on the day of enrollment into MISTIE III (Day 0) (for both medical and surgical patients) and daily for up to 4 days timed with routine collection of blood for daily blood tests (medical patients), or with hematoma fluid aspiration (surgical patients). Samples will be collected in two separate tubes, one shipped immediately and the other locally processed (centrifuged and aliquoted), frozen at -70°C, and shipped to specific investigators for storage and analysis.

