Finally, we propose to evaluate whether the difference in neurologic outcome between the MISTIE III intervention and control is greatest in those with CMBs on GRE-MRI. Secondary analyses will examine the interaction between CMBs, Spot Sign, white matter burden, and neurologic outcome. The model for clinical benefit (i.e. mRS 0-3 vs. 4-6) will include effects for treatment, CMBs, and the interaction between treatment and CMBs. Wald's test will be used to assess the significance of the interaction effect. These results can be confirmed using the CMH test.

**Specific Aim 3a/b.** To identify the association between acute phase levels of intracranial and peripheral inflammatory mediators and hematoma volume, peri-hematomal edema and neurologic outcomes as determined by cerebral imaging and mRS.

The primary outcome measure of this aim is serial levels of inflammatory mediators in hematoma fluid/surgical aspirate. The secondary outcome measures are: (i) ICH/IVH clot burden on admission and end of treatment and absolute/relative perihematoma edema (PHE) at admission and end of treatment (24 hrs post brain catheter removal) compared to time of brain catheter placement; (ii) functional outcomes measured by mRS at 90 and 180 days after admission; and (iii) serial levels of inflammatory mediators in serum. Hematoma aspirate and serum inflammatory markers (see Table below) will be determined by the following methods:

White blood cell count and differential, CRP, glucose, protein, red blood cell count, fibrinogen, and fibrin D-dimer (DD) will be measured using routine laboratory assays.

Concentrations of IL-1 $\alpha$ , IL-2, IL-6, TNF $\alpha$ , IL-8, IL-10, (MCP)-1, (MIP)-1 $\alpha$ , IL-1 receptor antagonist, IL-10, TGF- $\beta$  and IFN $\gamma$  will be quantified using immunoassays.

Levels of matrix metalloproteinases (MMPs) will be assayed by two-step sandwich enzyme-linked immunosorbent assay methods.

Glutamate concentrations will be analyzed by high-performance liquid chromatography.

Inflammatory Marker Studies	
Serum Studies	D-dimer, C-reactive protein (CRP), fibrinogen, matrix metalloproteinases (MMPs), Interleukin-6 (IL-6), tumor necrosis factor- $\alpha$ (TNF- $\alpha$ ), glutamate

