Hematoma Aspirate Studies	White blood cell count and differential, glucose, protein, red blood cell count, Interleukin-1 (IL-1), Interleukin-2 (IL-2), Interleukin-6 (IL-6), Interleukin-8 (IL-8), IL-10, monocyte chemoattractant protein(MCP)-1, macrophage inflammatory protein (MIP)-1 $\alpha$ , tumor necrosis factor- $\alpha$ (TNF $\alpha$ ), Interferon-gamma (IFN $\gamma$ ), transforming growth factor(TGF)- $\beta$ , matrix metalloproteinases (MMPs)

Statistical plan: Analysis of categorical variables will be performed using the Pearson's Chi-square test. The Fisher exact test will be used when applicable. Continuous variables will be analyzed using one-way Analysis of variance if data is normally distributed or with Kruskal-Wallis test if not normally distributed. Trend statistic of inflammatory markers will be calculated using the Mantel-Haenszel test for linear association, with the catheter day plotted on the X-axis and levels of specific inflammatory mediators on the Y-axis.

For analysis of secondary outcome measures, inflammatory markers will be expressed as AUC (area under the curve) and included in a multifactorial linear regression model to test for associations with ICH/IVH/PHE volumes and with 90/180-day mRS. The models will include age, sex, and ICH score as covariates. Given the anticipated small sample size of the study population, a total of four or fewer confounders can be controlled in regression models. All tests will be two-tailed, with significance defined by  $p < 0.05$ . Statistical analysis will be performed using STATA 12.0 (Stata, College Station, Texas).

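### Ancillary Aim 3a/b does not say which arms the serum-marker regressions use and lists no term for treatment arm, so if both arms are used, a marker shifted by treatment can show a spurious link with end-of-treatment clot volume and edema.

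*Protocol*

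**What the plan says.** All of this is in Protocol Appendix 8 (MTI-M3) unless noted.

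- **Exposure.** Section 7, Specific Aim 3a/b: "inflammatory markers will be expressed as AUC (area under the curve) and included in a multifactorial linear regression model", to be tested against ICH/IVH/PHE volumes and 90/180-day mRS.
- **Covariates.** "The models will include age, sex, and ICH score as covariates". Because a small sample is expected, "a total of four or fewer confounders can be controlled in regression models". Three places are used, so one is free.
- **Test.** "All tests will be two-tailed, with significance defined by" p<0.05.
- **Markers.** The primary measure is markers in hematoma fluid or surgical aspirate. The secondary measures include "serial levels of inflammatory mediators in serum" (D-dimer, CRP, fibrinogen, MMPs, IL-6, TNF-alpha, glutamate).
- **Who gives serum.** Section 4, item c(i): on the day of enrollment "for both medical and surgical patients) and daily for up to 4 days". The serum AUC therefore spans surgery and dosing in one arm and medical care in the other.
- **Outcomes.** Clot burden and edema at admission and at end of treatment. End of treatment is dated from brain catheter removal and compared with catheter placement.
- **Arm in the other aims.** The clot-reduction analyses of Aims 1, 2 and 4a are said to focus on the surgical arm. The Spot Sign and microbleed outcome models include treatment. Aim 4b combines the arms and gives a reason. Aim 3 has no such sentence.

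**The concern.** Arm moves the imaging outcomes strongly in the sponsor's own phase II data. Table 3 in Section 2.2 gives Stage 2 end-of-treatment clot volumes of 41±17 mL (medical) and 18±14 mL (surgical). The Edema paragraph of Section 2.2 "shows a reduction of 22 ml of edema when compared to medical subjects in the same time frame", with a change of −22±35% surgical against +47±46% medical. An operation followed by intraclot fibrinolysis can plausibly also move serum D-dimer, fibrinogen, CRP or IL-6.

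If both arms are analysed together, arm is then a common cause of exposure and outcome. Age, sex and ICH score cannot stand in for it, because randomization makes baseline variables independent of arm apart from chance. An effect of surgery could be reported as an effect of inflammation, and a true association of the opposite sign could be hidden.

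**Working it through.** Aim 3a/b gives no sample size, power or detectable effect, so there is no stated figure to reproduce. The check is whether the mechanism is large enough to matter.

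**Inputs**
- End-of-treatment clot volume: 41±17 mL medical, 18±14 mL surgical, difference Δ = −23 mL (Table 3, Stage 2).
- Edema change: +47±46% medical, −22±35% surgical (Section 2.2, Edema).
- mRS 0-3 at 180 days: 24% medical, 35% surgical (Section 2.2, Functional Outcome Benefit).
- Admission volume: assumed 45±16 mL in both arms.
- Shift d of the marker caused by treatment: not in the documents; assumed 0.25, 0.5 and 1.0 within-arm SD.
- Number per arm: not in the documents, which say only that it will be small; 50 and 100 per arm shown, allocated 1:1.
- No association between marker and outcome within either arm.

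**Step 1: the spurious slope.** With 1:1 allocation and no arm term, the slope of volume on marker converges to

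0.25·d·Δ / (1 + 0.25·d²)

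- d = 0.25: −1.4375 / 1.0156 = −1.42 mL per SD
- d = 0.5: −2.875 / 1.0625 = −2.71 mL per SD
- d = 1.0: −5.75 / 1.25 = −4.60 mL per SD

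The true within-arm slope is zero in each case.

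**Step 2: how often it would be declared significant.** The pooled variance of volume is (17² + 14²)/2 + 0.25·23² = 242.5 + 132.25 = 374.75. For d = 0.5 the spurious correlation is −2.875 / √(1.0625 × 374.75) = −0.144. With 100 participants in total the expected test statistic is 0.144 × √98 / √(1 − 0.144²) = 1.44. The chance of passing 1.96 is then about 30%.

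**Step 3: simulation.** Repeated trials were generated and analysed by OLS with a two-sided test at 0.05. Three covariates unrelated to arm stood in for age, sex and ICH score. False-positive rates for end-of-treatment clot volume:

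| Per arm | d = 0.25 | d = 0.5 | d = 1.0 |
|---|---|---|---|
| 50, no arm term | 11% | 30% | 78% |
| 100, no arm term | 17% | 54% | 98% |
| either, arm included | about 5% | about 5% | about 5% |

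The approximation in Step 2 agrees with these to within about one percentage point.

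**Step 4: the other outcomes, no arm term**
- Edema change, d = 0.5 and 1.0: 34% and 84% with 50 per arm; 59% and 99% with 100 per arm.
- mRS 0-3: 5% to 8% with 50 per arm across the shifts. If treatment does not change mRS: 4% to 6%.
- Admission clot volume: 4% to 6%.
- No marker shift (d = 0): 4% to 6%, apart from simulation noise, for every outcome.

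With arm added, the rate was 4.0% to 6.4% in every setting simulated.

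**The case against.** **The arms may not be pooled at all.** Aim 3's primary measure is surgical aspirate, its trend tests run by catheter day, end of treatment is dated from the catheter, and the sample is expected to be small. If the serum regressions are surgical-only, arm is constant and this confounding disappears. This stands in part: pooling is an inference. It is still the better reading. The appendix says so when an analysis focuses on the surgical arm, and Aim 3 does not; serum is also collected from medical patients. On either reading the analysis set is unstated.

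**The marker shift is assumed.** This stands. No document gives the effect of surgery or rt-PA on any serum marker, so the rates above are a range and not a prediction.

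**Arm may act on the marker through clot volume.** If less clot means less inflammation, part of the between-arm association is real, and adjusting for arm removes it. This stands as a point about interpretation. The adjusted coefficient answers a narrower, within-arm question, and the plan should say so. It does not rescue the unadjusted model, which cannot separate that route from a direct effect of the procedure or drug on the marker.

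**A stronger reading is tempting.** A reader might infer that every marker moved by treatment will appear related to clot volume, edema and outcome alike. The documents do not support that. Treatment must shift both marker and outcome, and detection depends on the size of the shift and on numbers. Admission volumes precede treatment, and the mRS effect is small. Calculations at full trial enrollment of 250 per arm look more dramatic, but they do not fit a plan that anticipates a small sample in an optional study.

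**Conclusion.** The point holds conditionally. The Aim 3a/b covariate list omits treatment arm and the serum analysis set is not stated. If both arms are used, end-of-treatment clot volume and edema are exposed to confounding by arm: about 30% false positives for clot volume at an assumed 0.5 SD marker shift with 50 per arm, against a nominal 5%. This rests on the phase II volumes, the assumed shift and sample sizes, and no within-arm association. The mRS analyses are little affected, and admission volumes not at all.

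It would be wrong to infer that the trial's conclusions are at risk. These are secondary analyses in an optional, observational ancillary study, and the primary, safety and monitoring analyses do not depend on them. It is worth correcting because the remedy is simple and fits within the plan's own limit on confounders.

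**What to change.** In Appendix 8, Section 7, Specific Aim 3a/b, replace the covariate sentence with wording such as: *Serum-marker models use participants from both arms and include age, sex, ICH score and randomized treatment arm; the marker coefficient is interpreted as a within-arm association. Aspirate-marker models use the surgical arm only and include age, sex and ICH score.*

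Also define the end-of-treatment imaging time for medical subjects, who have no catheter placement or removal to date it from. Without this, the end-of-treatment outcomes are undefined for half of a pooled analysis even with arm in the model.

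Arm takes the fourth and last confounder place the plan allows. The cost is one degree of freedom, and between-arm variation in clot volume no longer contributes to the estimate. No new data are needed, and the aspirate analyses do not change.

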**Specific Aim 4a. ApoE Genotype**

Secondary analyses will explore whether imaging and genetics are associated with specific subcategories of neurological complications, whether they predict improved neurological outcome, and whether they stratify who will receive the most clinical benefit from the MIS intervention

We will test the hypothesis that specific ApoE genotype predicts successful clot reduction after MIS. This analysis will focus on the surgical management arm. We predict those patients with an E2 allele will have less clot reduction. Similar to Aim 1a, clot reduction will be analyzed as a continuous variable compared using a two-sample t-test, and as a dichotomized variable compared using a chi-square test. We expect 9% of patients will have an ApoE E2 allele. Assuming a SD of 30% and a sample size of 22 and 228 for presence of an ApoE E2 allele vs. absence, respectively, the study will have 80% power to detect a mean difference of 18.8% in clot size reduction. When dichotomized at 60%, the study will have 84% power to detect a difference of 24% (22% for the ApoE E2 allele group and 56% for the no ApoE E2 allele group) with a 0.05 two-sided significance level.

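### Appendix 8, Aim 4a: the ApoE power statement gives a 24-point difference, but its own rates (22% and 56%) differ by 34 points, and a 24-point difference would have only about 50–60% power

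*Protocol*

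**What the plan says.** Specific Aim 4a in Section 7 of Appendix 8 tests whether carrying an ApoE E2 allele predicts less clot reduction in the surgical arm. Clot reduction is analysed first as a continuous variable and then, split at 60%, "as a dichotomized variable compared using a chi-square test".

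The planning inputs are all printed in that paragraph. On prevalence: "We expect 9% of patients will have an ApoE E2 allele". On group sizes: "a sample size of 22 and 228 for presence of an ApoE E2 allele vs. absence". The test is run "with a 0.05 two-sided significance level".

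For the dichotomised version the claim is "84% power to detect a difference of 24% (22% for the ApoE E2 allele group and 56% for the no ApoE E2 allele" group, so the effect and the two success rates behind it stand in one sentence.

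**The concern.** The sentence contradicts itself. The difference between the two success rates is 34 points, yet the effect the study is said to detect is 24 points. Both cannot be the basis of one power figure.

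The power statement tells later readers how to interpret a null genotype result. Taken at face value, this one says that a 24-point effect of the E2 allele would be found five times in six. If the 84% really belongs to 34 points, a null result says little about a 24-point effect, and reporting that such an effect had been excluded would be wrong. Appendix 8 presents its markers as a way to identify which patients are likely to benefit from the procedure, so the detectable effect should be stated correctly.

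**Working it through.** **Inputs** (all from Appendix 8, Specific Aim 4a): n1 = 22 with E2, n2 = 228 without E2, two-sided alpha 0.05 (z = 1.96), p1 = 0.22, p2 = 0.56. The total of 250 is the whole surgical arm, with no allowance for missing genotype or imaging.

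**Step 1: subtraction.** 56 − 22 = 34 points. The other dichotomised power statements in the appendix give the plain difference of their rates: Spot Sign 60 − 40 = 20, patients without a Spot Sign 44 − 27 = 17, microbleeds 67 − 47 = 20, haptoglobin 46 − 27 = 19. Only the ApoE sentence fails.

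**Step 2: reproduce the stated 84%.** Use the continuity-corrected normal approximation

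power = Φ[(d − c − 1.96·SE0) / SE1],

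where d is the absolute difference in rates, c = (1/n1 + 1/n2)/2, SE0 = √[p̄(1 − p̄)(1/n1 + 1/n2)], SE1 = √[p1(1 − p1)/n1 + p2(1 − p2)/n2], and p̄ is the patient-weighted mean rate.

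- c = (0.04545 + 0.00439)/2 = 0.0249
- p̄ = (22 × 0.22 + 228 × 0.56)/250 = 0.5301
- SE0 = √(0.2491 × 0.04984) = 0.1114, so 1.96·SE0 = 0.2184
- SE1 = √(0.00780 + 0.00108) = 0.0942
- (0.34 − 0.0249 − 0.2184)/0.0942 = 1.03, giving power 84.8%

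Exact enumeration of the continuity-corrected chi-square test gives 85.0%. Without the correction, power for these rates is higher: 90.2% (pooled normal approximation), 89.7% (exact Pearson), 88.6% (Fisher).

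The same corrected formula comes close to the appendix's other claims, which suggests it is the one that was used:

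| Comparison | Stated | Continuity-corrected |
|---|---|---|
| Spot Sign, 85 vs 165, 40% vs 60% | 82% | 82.3% |
| Microbleeds, 77 vs 173, 67% vs 47% | 80% | 80.6% |
| Haptoglobin, 65 vs 435, 46% vs 27% | 82% | 83.0% |
| No Spot Sign, 165 vs 165, 27% vs 44% | 87% | 87.9% |
| ApoE, 22 vs 228, 22% vs 56% | 84% | 84.8% |

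**Step 3: are the printed rates the intended ones?** Their weighted mean, 53.0%, equals the 53% overall success rate that the appendix assumes under Specific Aim 2 (white matter disease). The Spot Sign pair averages (85 × 0.40 + 165 × 0.60)/250 = 53.2%, and the microbleed pair (77 × 0.67 + 173 × 0.47)/250 = 53.2%. The rates are therefore consistent with the rest of the appendix. The odd figure is the 24.

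**Step 4: power for a true 24-point difference.** The appendix gives no 24-point pair, so I hold one printed rate fixed and move the other. Both pairs are assumptions.

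For 32% vs 56%: p̄ = 0.5389, 1.96·SE0 = 0.2181, SE1 = 0.1047, and (0.24 − 0.0249 − 0.2181)/0.1047 = −0.03, giving 48.8%.

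For 22% vs 46%: p̄ = 0.4389, 1.96·SE0 = 0.2171, SE1 = 0.0943, and (0.24 − 0.0249 − 0.2171)/0.0943 = −0.02, giving 49.1%.

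| Method | 22% vs 56% | 32% vs 56% | 22% vs 46% |
|---|---|---|---|
| Continuity-corrected | 84.8% | 48.8% | 49.1% |
| Exact, corrected chi-square | 85.0% | 50.6% | 50.3% |
| Fisher exact | 88.6% | 56.7% | 58.5% |
| Pooled normal | 90.2% | 58.3% | 59.6% |
| Exact Pearson | 89.7% | 59.1% | 61.1% |
| Arcsine | 89.3% | 59.0% | 63.5% |
| Unpooled normal | 95.0% | 63.0% | 72.1% |

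No method brings either 24-point pair to 84%. A one-sided pooled test reaches only 71% and 73%.

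A third choice keeps the overall rate at 53%: p2 = 0.53 + (22/250) × 0.24 = 0.551 and p1 = 0.311. This lies between 29% vs 53% and 32% vs 56%, where the corrected formula gives 48.6% and 48.8%.

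**The case against.** The strongest reply is that this is a one-digit slip and not a faulty power calculation. The group sizes, rates, significance level and power all fit together, and only the printed subtraction is wrong. The rates stand directly after the wrong figure, so a careful reader can recover the right effect. That is correct, and it is why the point is minor.

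A second reply is that the 50–60% range rests on rate pairs the appendix never states and varies with the method, from about 49% to 72% across everything tried. This also stands as a caution. Pairs with a rate close to 0% or 100% would have more power still (75% vs 99% gives 93% with the corrected formula), but they are incompatible with an overall success rate of 53%. For the two pairs tied to a printed rate, the chi-square calculations, corrected or uncorrected, run from 49% to 61%.

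Third, the aim also has a continuous analysis, with 80% power for a mean difference of 18.8% at an SD of 30%. That figure checks: 18.8/(30 × √0.04984) − 1.96 = 0.85, giving 80%. Only the dichotomised statement is affected.

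Finally, if 34 was intended, 24 points was never a target, and nothing obliges the appendix to report power for it. I agree, so that addition is optional. None of these replies makes the sentence right as printed.

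**Conclusion.** The concern holds. The printed difference of 24% is wrong for the printed rates; the correct figure is 34%. The 84% power is sound for 22% versus 56% with 22 and 228 patients, and becomes 85–90% with exact chi-square tests. For 24 points, power is about 50–60%: 49–51% with the continuity correction and 58–61% with the uncorrected pooled or Pearson test, assuming 32% vs 56% or 22% vs 46%. The stated effect is therefore about 29% smaller than the one the power supports (10/34).

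That 34 was the intended figure is an inference, but three things support it: the power reproduces from the printed rates, those rates average to the appendix's 53%, and every other such statement in the appendix is a plain subtraction. The consequence is limited to one secondary genetic comparison in an optional, observational ancillary study. It sets no sample size and does not affect the main trial's endpoint, power, boundaries or safety monitoring.

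**What to change.** In Appendix 8, Section 7, Specific Aim 4a, replace the 24% difference with 34%, leaving the rates, group sizes and 84% power as they are. If the authors want readers to be able to interpret a smaller effect, add that power for a 24-point difference is about 50–60%, naming the rate pair and test used. Should 24 points turn out to be the real target, the rates and the power must both be restated.

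The cost is one figure. The stated detectable effect becomes less favourable, but design, sample size and analysis do not change.
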